9.2.1.6 Visit 6 - Safety Follow up Call (Day 71) (± 3 days)

This visit is required for patients who do not enter the OLE study on Day 34, or who withdraw from the study early. This visit should occur four weeks after Visit 5, (± 3 days) or withdrawal from treatment, and can be conducted over the telephone. The following observations will be made on Day 71: concomitant medications (including AEDs) and AEs.

9.2.2 Open Label Extension

Patients who enter the OLE will be dispensed IMP at Visit 4 (Day 34) and will have regular clinic visits for a maximum of one year or earlier (if marketing authorization is granted or the patient withdraws). The visit schedule is calculated relative to Visit 4 (Day 34).

9.2.2.1 Visit 5 (Open Label Extension) - Two Weeks (± 3 days)

This visit will occur two weeks after Visit 4 (Day 34). Patients will return all used and unused IMP. The following observations will be made at Visit 5 (OLE): concomitant medications (including AEDs), physical examination (including body weight), ECG, vital signs, review of seizure diary and AEs.

Clinical laboratory samples (blood and urine) will be taken for hematology, biochemistry and urinalysis. The C-SSRS will be administered. The investigator must record the patient's attendance at the visit and the outcome.

The investigator must assess adherence to the dosing regimen and recording of rescue medications by reviewing the patient's diary.

9.2.2.2 Visit 6 (Open Label Extension) - One Month (± 3 days)

This visit will occur one month after Visit 4 (Day 34). Patients will return all used and unused IMP. The following observations will be made at Visit 6 (OLE): concomitant medications (including AEDs), physical examination (including body weight), ECG, vital signs, review of seizure diary and AEs.

Clinical laboratory samples (blood and urine) will be taken for hematology, biochemistry and urinalysis. The C-SSRS will be administered. The investigator must record the patient's attendance at the visit and the outcome.

The investigator must assess adherence to the dosing regimen and recording of rescue medications by reviewing the patient's diary.

9.2.2.3 Visit 7 (Open Label Extension) - Two Months (± 3 days)

This visit will occur two months after Visit 4 (Day 34). Patients will return all used and unused IMP. The following observations will be made at Visit 7 (OLE): concomitant medications (including AEDs), physical examination (including body weight), ECG, vital signs, review of seizure diary and AEs.

Clinical laboratory samples (blood and urine) will be taken for hematology, biochemistry and urinalysis. The C-SSRS will be administered. The investigator must record the patient's attendance at the visit and the outcome.

The investigator must assess adherence to the dosing regimen and recording of rescue medications by reviewing the patient's diary.

9.2.2.4 Visit 8 (Open Label Extension) - Three Months (± 7 days)

This visit will occur three months after Visit 4 (Day 34). Patients will return all used and unused IMP. The following observations will be made at Visit 8 (OLE): concomitant medications (including AEDs), physical examination (including body weight), ECG, vital signs, review of seizure diary and AEs.

Clinical laboratory samples (blood and urine) will be taken for hematology, biochemistry and urinalysis. The C-SSRS will be administered. The investigator must record the patient's attendance at the visit and the outcome.

The investigator must assess adherence to the dosing regimen and recording of rescue medications by reviewing the patient's diary.

9.2.2.5 Visit 9 (Open Label Extension) - Six Months (± 7 days)

This visit will occur six months after Visit 4 (Day 34). Patients will return all used and unused IMP. The following observations will be made at Visit 9 (OLE): concomitant medications (including AEDs), physical examination (including body weight), ECG, vital signs, review of seizure diary and AEs.

Clinical laboratory samples (blood and urine) will be taken for hematology, biochemistry and urinalysis. The C-SSRS will be administered. The investigator must record the patient's attendance at the visit and the outcome.

The investigator must assess adherence to the dosing regimen and recording of rescue medications by reviewing the patient's diary.

9.2.2.6 Visit 10 (Open Label Extension) - Nine Months (± 7 days)

This visit will occur nine months after Visit 4 (Day 34). Patients will return all used and unused IMP. The following observations will be made at Visit 10 (OLE): concomitant medications (including AEDs), physical examination (including body weight), ECG, vital signs, review of seizure diary and AEs.

Clinical laboratory samples (blood and urine) will be taken for hematology, biochemistry and urinalysis. The C-SSRS will be administered. The investigator must record the patient's attendance at the visit and the outcome.

The investigator must assess adherence to the dosing regimen and recording of rescue medications by reviewing the patient's diary.

9.2.2.7 Visit 11 (Open Label Extension End of Treatment) - Twelve Months (± 7 days)

This visit will occur twelve months after Visit 4 (Day 34). Patients will return all used and unused IMP. The following observations will be made at Visit 11 (OLE): concomitant medications (including AEDs), physical examination (including body weight), ECG, vital signs, review of seizure diary and AEs.

Clinical laboratory samples (blood and urine) will be taken for hematology, biochemistry and urinalysis. The C-SSRS will be administered. The investigator must record the patient's attendance at the visit and the outcome.

The investigator must assess adherence to the dosing regimen and recording of rescue medications by reviewing the patient's diary.

Starting at Visit 11, patients will begin to taper down their IMP dose. The dose will be reduced by 10% of their OLE maintenance dose per day.

9.2.2.8 Visit 12 (Open Label Extension End of Taper)

This visit will be ten days after Visit 11. All IMP (used and unused) will be collected and a check of the returned IMP against usage must be made. A physical examination (including body weight), ECG and vital signs will be assessed and the C-SSRS will be administered. The trained investigator or study coordinator will complete the Study Medication Use and Behavior Survey as an interview with the patient/caregiver.

Clinical laboratory samples (blood and urine) will be taken for hematology, biochemistry and urinalysis and a review of concomitant medications (including AEDs) and AEs will be completed. Patient diaries will be collected and reviewed.

9.2.2.9 Safety Follow Up Call (± 3 days)

This visit will occur one month after the OLE End of Taper and can be conducted over the telephone. The following observations will be made during the follow up call: concomitant medications (including AEDs) and AEs.

10. WITHDRAWAL

In accordance with the Declaration of Helsinki³¹, the FDA regulations relating to good clinical practice (GCP) and clinical trials^{32,33,34}, the EU Clinical Trials Directive (2001/20/EC)³⁵ and/or other applicable regulations, a patient has the right to withdraw from the study at any time and for any reason without prejudice to his or her future medical care by the physician or at the institution.

The patient must be withdrawn from the study if any of the following apply:

- Administrative decision by the investigator, GW, or a Regulatory Authority.
- Pregnancy.
- Protocol deviation that is considered to potentially compromise the safety of the patient.
- Withdrawal of patient consent.
- Withdrawal of legal representative consent.
- Lost to follow up.
- ALT $>3 \times$ ULN or AST $>3 \times$ ULN **and** (TBL $>2 \times$ ULN **or** INR >1.5).
- ALT or AST $>3 \times$ ULN with the appearance of fatigue, nausea, vomiting, right upper quadrant pain or tenderness, fever, rash, and/or eosinophilia ($>5\%$).
- ALT or AST $>8 \times$ ULN.
- ALT or AST $>5 \times$ ULN for more than two weeks.
- Any other IMP is taken as part of a clinical trial during the study.

Patients may also be withdrawn from the study for any of the following:

- Patient non-compliance.
- AE, which in the opinion of the investigator, would compromise the continued safe participation of the patient in the study.
- Any evidence of drug abuse or diversion.
- Suicidal ideation or behavior of type four or five during the treatment period, as evaluated with the C-SSRS.

Should a patient request or decide to withdraw from the study, all efforts must be made to complete and report the observations as thoroughly as possible up to the date of withdrawal. Patients who withdraw should have their dose of IMP tapered gradually (10% each day) over a period of 10 days, beginning at the time the decision

is made to discontinue. In some cases, tapering the dose of IMP may be inadvisable (e.g., continued dosing is not possible due to an AE). The decision on whether or not to taper IMP will be left to the investigator's clinical judgment. All assessments required at Visit 4 (if the withdrawal is during the blinded phase) or Visit 11 (if the withdrawal is during the OLE) should be conducted if possible. If the tapered dose is administered, patients should return for Visit 5 (if withdrawal is during the blinded phase) or Visit 12 (if the withdrawal is during the OLE) if possible. Wherever possible, the safety follow-up visit should be conducted 28 days from the date of the last dose of IMP. Patients withdrawing due to an AE should be followed up according to [Section 12.7](#). All information should be reported on the applicable CRF pages

11. URGENT SAFETY MEASURES

The sponsor and investigator may take appropriate urgent safety measures in order to protect the patients of a clinical trial against any immediate hazard to their health or safety. If such measures are taken by the investigator they must notify GW immediately or at least within 24 hours of awareness. GW will report urgent safety measures to Competent Authorities by telephone within 24 hours of awareness, wherever possible, and will provide a written report to the Competent Authorities and IRB/EC within three days.

12. ADVERSE EVENT REPORTING

12.1 Definitions

12.1.1 Adverse Event

For the purposes of this study an AE is defined as:

Any new unfavorable/unintended signs/symptoms (including abnormal laboratory findings), or diagnosis or worsening of a pre-existing condition, which is present following screening (Visit 1) throughout the study and up to the post treatment, safety follow-up visit (28 days after last dose of IMP), which may or may not be considered to be related to the IMP. Any event that is the result of a study procedure must be recorded as an AE.

Surgical/Investigational procedures are not AEs. The medical reason for the procedure is the AE. Elective hospitalizations for pre-study existing conditions or elective procedures are not AEs. The exception may be if the patient has an AE during hospitalization which prolongs their scheduled hospital stay in which case it would be considered a SAE (refer to [Section 12.2](#)).

If reporting a fatal event, the SAE term should be the underlying cause of the death (e.g., disease or medical condition leading to death).

12.1.2 Investigator

The term ‘investigator’ refers to the study PI or a formally delegated study physician.

12.2 Serious Adverse Events

During clinical investigations, AEs may occur which, if suspected to be IMP related, might be significant enough to lead to important changes in the way the IMP is developed (e.g., change in dose, population, monitoring need, consent forms). This is particularly true for events that threaten life or function. Such SAEs will be reported promptly to Regulatory/Competent Authorities, applicable IRB/ECs and Investigators (expedited reporting) by GW.

An AE must only be classed as serious i.e., an SAE, when the event falls into one of the following criteria:

- Results in death.
- Is life-threatening.*
- Requires inpatient hospitalization or prolongation of existing hospitalization.
- Results in persistent or significant disability/incapacity.
- Is a congenital anomaly/birth defect.
- Medically significant.**

* The term “life-threatening” in the definition of “serious” refers to an event in which the patient was at risk of death at the time of the event; it does not refer to an event, which hypothetically might have caused death if it were more severe.

** Medical and scientific judgment should be exercised in deciding whether SAE reporting is appropriate in other situations. Important medical events may not be immediately life threatening or result in death or hospitalization but may jeopardize the patient or may require intervention to prevent one of the other outcomes listed in the definition above. These should also usually be considered serious. Examples of such events are intensive treatment in an emergency room or at home for allergic bronchospasm; blood dyscrasias or convulsions that do not result in hospitalization; or development of drug dependency or drug abuse.

12.3 Reporting Procedures for Serious Adverse Events

All SAEs occurring during the study must be reported to GW with any other supporting information and recorded in the AE section of the CRF. Any on-going

SAEs should be followed up until resolution wherever possible. For all deaths, the working diagnosis or cause of death as stated on a death certificate, available autopsy reports and relevant medical reports should be sent to GW promptly.

All SAEs must be reported directly to GW PVD within 24 hours of discovery or notification of the event. All SAE information must be recorded on the SAE forms provided in the site files and faxed to GW PVD. Additional information received for a case (follow-up or corrections to the original case) need to be detailed on a new SAE form, signed/dated and faxed to the GW PVD and the AE section of the CRF must be updated.

The investigator should continue to document all AEs which occur up to the last formal follow-up visit (Visit 13 for patients entering the OLE and Visit 6 for those patients that are not entering the OLE). If the investigator subsequently becomes aware of any deaths or a new IMP-related SAE after the last formal follow-up period of the study, these should still be reported to the GW PVD.

Any other problem discovered outside these time limits which is deemed to be an unexpected safety issue and is likely to have an impact on patients who have participated in the study, then these should be treated as an SAE and reported to GW PVD. Such post study SAEs do not need to be recorded on the patient's CRF if editing rights to the CRF have been removed.

Contact details for the GW PVD are provided at the front of the site files for all study centers, and upon the GW SAE Report form.

12.4 Pregnancy

Any patient, or patient's partner, who has become pregnant whilst receiving IMP, or within 90 days of last dose of IMP, must be reported to the GW PVD within 24 hours of first awareness. Please use the GW Pregnancy Monitoring Forms provided. Where possible the investigator should provide the outcome of the pregnancy.

The investigator is not obliged to actively monitor for any pregnancies that commence more than 90 days after the final dose of IMP. However, if the investigator becomes aware of a new pregnancy outside this time limit then they should report it as above. GW PVD will follow up for all pregnancy outcomes.

12.5 Causality Assessment

Causality assessment is required for all AEs and SAEs. Causality assessment must only be assigned by the investigator. All cases judged as having a reasonable suspected causal relationship to the study medication must be reported as such. The

expression “*reasonable causal relationship*” is meant to convey in general that there are facts (evidence) or arguments to suggest a causal relationship.

The following question which must be answered by the investigator for all AEs is used to capture the reasonable causal relationship of an event to the study medication:

“In your opinion is there a plausible relationship to the study medication?” The answer is “yes” or “no”.

Events that start before the first dose of study medication (pre-treatment) should be considered as not causally related. Where a pre-treatment event worsens in severity following the first dose of study medication, a new event record should be entered into the CRF.

Considering the explanation given above, investigators are strongly encouraged to express their opinion on what the cause of an AE might be. For individual patients, the investigator is usually in the best position to assess the underlying suspected cause of an AE. For all AEs and especially SAEs, it is important that the investigator assess not only the possible role of the study medication but also competing etiological factors as the underlying cause. Factors for consideration may include:

- Medical history.
- Lack of efficacy/worsening of treated condition.
- Concomitant or previous treatment.
- Withdrawal of study medication.
- Protocol-related procedure.

12.6 Reporting Procedures for All Adverse Events

All AEs* (including SAEs) occurring during the study will be reported on the running logs in the AE section of the CRF. This includes all events from the time following screening (Visit 1) to post study follow-up (Visit 13 for patients entering the OLE and Visit 6 for those patients that are not entering the OLE), whether or not attributed to IMP and observed by the investigator or patient.

*For the patient’s expected seizure types, these do not routinely require documentation as AEs. However, any worsening, including change in the pattern or severity of seizures must be documented as an AE. Any AE which meets SAE criteria should still be reported as a SAE.

The following information will need to be provided for all AEs:

A) Adverse Event (Diagnosis or Syndrome if known, or Signs and Symptoms)

Where the investigator cannot determine a diagnosis, signs or symptoms should be recorded on the AE section of the CRF. Once a diagnosis has been determined the AE section of CRF must be updated to reflect the diagnosis in replacement of the original symptoms. In circumstances where only a provisional diagnosis is possible (working diagnosis), the CRF must be updated to reflect the provisional diagnosis in replacement of the original symptoms. In some circumstances it may be relevant for the investigator to include the symptoms alongside the diagnosis in the verbatim event description. However, the diagnosis (full or provisional) should be clearly stated e.g., fever and malaise due to a respiratory tract infection.

B) Adverse Event Start Date and Stop Date

The start and stop dates of the event must be provided. All AEs require these fields to be completed in full. Partial dates or missing dates are not normally acceptable and significant effort must be undertaken to obtain any unknown information. If a precise date is not known an estimated date should be provided instead. When a complete date cannot be given then record as much information as possible (i.e., month and year or in exceptional circumstances just year). When the actual start date becomes known the CRF must be updated to replace the previously recorded date.

C) Outcome

The outcome of the event must be recorded accurately and classified into one for the following categories:

- Recovered.
- Recovered with sequelae.
- Continuing.
- Patient died.

D) Severity

When describing the severity of an AE the terms mild, moderate, or severe should be used. Clinical judgment should be used when determining which severity applies to any AE.

If the severity of an AE fluctuates day-to-day, for example, a headache or constipation, the change in severity should not be recorded each time, instead only the worst observed severity should be recorded with AE start and stop dates relating to the overall event duration regardless of severity.

A severe AE is not the same as a SAE. For example, a patient may have severe vomiting but the event does not result in any of the SAE criteria above. Therefore it should not be classed as serious.

E) Causality

See [Section 12.5](#) above.

F) Action Taken with Study Medication

This question refers to the action taken with the IMP due to an AE. The action with the IMP must be classed as:

- None.
- Dose reduced temporarily.
- Dose reduced.
- Study medication interrupted.
- Study medication stopped.

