13.6.4.2 Adverse Events

AEs will be coded according to the Medical Dictionary for Regulatory Activities dictionary.

A treatment emergent AE is one that started, or worsened in severity or seriousness, following the first dose of IMP.

Descriptive presentations of treatment emergent AEs will be given by preferred term and system organ class for the safety analysis set. The number of patients reporting at least one AE will be provided. Summaries will be provided for each phase of the study separately.

The following summaries will be produced:

- All-causality AEs.
- Treatment related AEs.
- All-causality AEs by severity.
- All-causality serious AEs.
- Treatment related serious AEs.
- AEs reported as leading to permanent cessation of study treatment.
- Fatal AEs.

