USA	United States of America
VNS	Vagus Nerve Stimulation

Definition of Terms

Term	Definition
Baseline period	The period from screening (Visit 1) to enrollment (Visit 2).
Convulsive seizures	Tonic-clonic, tonic, clonic or atonic seizures.
Countable partial seizures	Partial/focal seizures with a motor or behavioral component that allow such seizures to be easily identified and hence counted.
Day 1	The day a patient is enrolled and begins PK sampling.
End of treatment	Completion of the treatment period (Visit 5 or Visit 12) or withdrawal.
End of study	Last patient's last visit / last contact.
IMP	Investigational Medicinal Product (Study Medication). Used to describe both investigational active product and reference therapy (placebo).
INR	International Normalized Ratio (INR) is a calculation made to standardize prothrombin time.
Investigator	Study Principal Investigator or a formally delegated study physician.
Non-convulsive seizures	Myoclonic, partial or absence seizures.
Partial seizures	Partial (focal) seizures occur when the electrical activity remains in a limited area of the brain.
Status epilepticus	Seizures lasting for 30 minutes or longer.
Sub-types of seizures	Seizure sub-types can be tonic, clonic, tonic-clonic, atonic, myoclonic, absence (typical and atypical), countable partial and other partial.

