8.1.2 Dose Escalation and Dose Adjustments

Patients will enter the blinded phase of the study and will be up-titrated over ten days (Day 2 to Day 11) to a maintenance dose or equivalent of GWP42003-P/placebo of 20 mg/kg/day. If GWP42003-P is not tolerated then the dose can be reduced accordingly at the discretion of the investigator. The titration regimen is described in [Table 8.1.2-1](#).

Table 8.1.2-1 Dose Up-Titration Regimen*		
Day - GWP42003-P/Placebo (Blinded Period)	Day - GWP42003-P only (OLE**)	Dose Level (GWP42003-P or equivalent placebo)
2	34	2.5 mg/kg
3	35	2.5 mg/kg
4	36	5.0 mg/kg
5	37	5.0 mg/kg
6	38	7.5 mg/kg
7	39	7.5 mg/kg
8	40	10.0 mg/kg
9	41	10.0 mg/kg
10	42	15.0 mg/kg
11	43	15.0 mg/kg
12 onwards	44 onwards	20.0 mg/kg

*GWP42003-P /placebo is to be taken twice daily. Total daily doses are shown.

** Only patients who were taking placebo during the double-blind period will up-titrate according to this schedule during the OLE period. Those taking GWP42003-P during the double-blind period will down-titrate their blinded IMP whilst simultaneously up-titrating with GWP42003-P, thus maintaining a daily dose of 20 mg/kg/day GWP42003-P throughout.

The titration regimen defined above should be followed to the maximum dose (20 mg/kg/day). Should an AE occur during titration which is attributable to IMP or concomitant AED, then IMP dose should be reduced to the next lower dose. Any other changes in concomitant AED therapy should be reviewed with the medical monitor before being initiated.

For those patients who do not enter the OLE the dose of GWP42003-P/placebo will taper off over 10 days beginning on Day 34. The patient will reduce the dose by 10% of the maintenance dose each day and treatment will end on Day 43.

Patients who enter the OLE period will be transitioned to the OLE treatment over a 10-day period in order to maintain blinding, simultaneously down-titrating blinded GWP42003-P /placebo whilst up-titrating open-label GWP42003-P. As such, patients who were taking GWP42003-P during the blinded period will maintain their 20 mg/kg/day dose throughout the transition from the blinded period into the OLE period and patients who received placebo during the blinded period up-titrate slowly to the 20 mg/kg/day dose in the OLE period. After this has taken place, the

maintenance dose of GWP42003-P may be adjusted up or down at the discretion of the investigator to a maximum of 30 mg/kg/day (no minimum).

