13.4 General Considerations

Unless stated otherwise, continuous variables will be summarized showing the number of non-missing values (n), mean, standard deviation, median, minimum and maximum and categorical variables will be summarized showing the number and percentage of patients falling in each category. Summaries will be presented for data recorded pre-treatment, during each 25 day dosing phase (placebo and GWP42003-P) and during the OLE phase separately.

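### For a fluctuating adverse event that runs past Day 34, the CRF cannot show whether its worst severity arose in the blinded phase or on open-label GWP42003-P

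*Protocol*

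**What the plan says.** Four parts of the protocol bear on this point.

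- **Recording of severity.** Section 12.6 D covers one case: "If the severity of an AE fluctuates day-to-day, for example, a headache or constipation". Sites then do not log each change, and "only the worst observed severity should be recorded with AE start and stop dates relating to the overall event duration regardless of severity". The items that 12.6 collects for each AE are the term, start and stop dates, outcome, severity, causality and action taken with study medication. None of them dates a change in severity.
- **New records.** Section 12.5 has the only general rule that splits an event: "Where a pre-treatment event worsens in severity following the first dose of study medication, a new event record should be entered". Section 12.6 separately requires that worsening of the patient's expected seizure types be documented as an AE.
- **Treatment sequence.** The Definition of Terms makes placebo part of the investigational medicinal product (IMP), which is also called study medication. A placebo patient's first dose is thus placebo on Day 2. Under section 8.1.2, "patients who received placebo during the blinded period up-titrate slowly" in the OLE. Table 8.1.2-1 starts this at 2.5 mg/kg on Day 34 and reaches 20 mg/kg from Day 44.
- **Summaries.** Version 2, section 13.4, presents data "during each 25 day dosing phase (placebo and GWP42003-P) and during the OLE phase separately". Section 13.6.4.2 lists all-causality AEs by severity and adds: "Summaries will be provided for each phase of the study separately". It defines treatment emergence once: "A treatment emergent AE is one that started, or worsened in severity or seriousness, following the first dose of IMP". The text of 13.6.4.2 at hand is that of Version 1. The Version 2 text shown ends before that section, and the amendment log lists no change to it.

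**The concern.** The protocol asks for severity by phase, but for one class of event it tells sites not to keep the information that would assign severity to a phase. Section 12.5 already accepts that worsening across a treatment boundary needs its own record. The protocol applies this at the first dose of study medication and not on Day 34, which for placebo patients is the first exposure to active drug.

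The secondary endpoint is the safety and tolerability of GWP42003-P compared with placebo. A grade that arose on open-label GWP42003-P can end up in the placebo column of that comparison. The statistical analysis plan can choose how AEs are assigned to phases, but it cannot supply a date of worsening that the CRF did not collect.

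**Working it through.** **Step 1. Does any rule open a new record at OLE entry?**

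- The 12.5 rule needs an event that began before the first dose of study medication. For a placebo patient that dose was on Day 2, so an AE with onset between Day 2 and Day 33 is outside the rule.
- The treatment-emergent definition has the same single anchor. Worsening on Day 20 and worsening on Day 42 are both after the first dose, so the definition does not separate them.
- The seizure rule covers expected seizure types only.

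So for a non-seizure AE that fluctuates, nothing splits or dates the record at Day 34.

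**Step 2. What do the tables show?** Take an invented case built on headache, one of the protocol's own examples. A placebo patient has headache that fluctuates between mild and moderate from Day 20. It is first severe on Day 42, at 15 mg/kg in the OLE up-titration, and continues to fluctuate. Section 12.6 D gives one record: start Day 20, severity severe. The protocol text shown does not say how AEs are assigned to phases, so both usual rules are tried.

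| Assignment | Placebo column, blinded phase | OLE column |
|---|---|---|
| By start date, one record | severe | nothing |
| By overlap of start and stop dates, one record | severe | severe |
| New record dated from the worsening | moderate | severe |

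The placebo column is wrong under both single-record rules. The OLE column is wrong only under start-date assignment. For an active patient whose AE reaches a higher grade in the OLE, the same steps place that grade in the blinded active column.

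**Step 3. Size.** The inputs are 20 patients (section 13.1) and 4:1 randomization (section 7.2). The plan states no figure of its own on this point.

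- Active: 20 × 4/5 = 16. Placebo: 20 × 1/5 = 4.
- One misplaced event in a placebo patient: 1/4 = 25 percentage points.
- One misplaced event in an active patient: 1/16 = 6.25 percentage points.
- Placebo patients with a severe AE, for one such case: 1/4 as recorded (exact 95% CI 0.6% to 80.6%), against 0/4 with a dated record (0% to 60.2%).

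**Step 4. How likely is a case?** The documents give no rate. Let q be the assumed chance that a placebo patient has such an event, with all 4 entering the OLE. The chance of at least one is 1 − (1 − q)^4.

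| q (assumed) | At least one of 4 |
|---|---|
| 5% | 18.5% |
| 10% | 34.4% |
| 20% | 59.0% |
| 30% | 76.0% |

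**The case against.** The strongest reply is that the rule is narrow and the harm is not shown. Most of its parts stand and limit the point.

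- **Every AE.** A reader might infer that 12.6 D governs all AEs. It governs day-to-day fluctuation. For a sustained step up after Day 34 the text is silent, and the AE definition in 12.1.1, which includes worsening of a pre-existing condition, could be read to allow a new entry. Nor is every AE open on Day 34 affected: it must fluctuate and later exceed its earlier worst grade.
- **Certain loss from the OLE.** A reader might infer that the event is always missed there. That needs assignment by start date, which the text shown does not state and which a statistical analysis plan may settle. The misplaced grade in the placebo column does not depend on that choice.
- **A bias in favor of GWP42003-P.** A reader might infer that the drug looks safer throughout. The documents do not support this. In active patients the same rule makes GWP42003-P look worse in the blinded phase. If the chance of a misplaced worsening were equal in the two arms, each rate would rise by about the same amount. A net bias needs a higher chance in placebo patients. That is plausible because they newly start active drug, but the documents give no figure.
- **Data lost for good.** Daily diaries and AE review at each visit may leave the date of worsening in source documents. This stands for source data. It does not put the date on the CRF record from which the tables are made.
- **Descriptive analysis.** Section 13.1 calls the analysis descriptive, and no safety decision rule depends on this count. That limits the consequence. It does not make the table correct.

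**Conclusion.** The point holds for non-seizure AEs whose severity fluctuates from day to day and which continue past Day 34. For these the CRF cannot show in which phase the worst severity occurred, although the summaries are to be split by phase and by severity. In placebo patients the result is a severity count that can include a grade reached on GWP42003-P. At most 4 patients can contribute, and each would move the placebo rate by 25 percentage points. In active patients the blinded rate can be inflated by 6.25 points per patient.

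The conclusion assumes that the Version 1 text of 13.6.4.2 still applies, as the amendment log suggests, and that sites follow 12.6 D across OLE entry as it is written. Neither the frequency of such events nor a net direction of bias can be derived from the documents. The change is worth making because it is cheap and because a placebo column of 4 patients leaves no room for a misplaced event.

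**What to change.** Make three linked changes.

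1. In 12.6 D, limit the single-record, worst-severity rule to fluctuation within one study phase.
2. In 12.5, add that when an AE ongoing at the first open-label dose afterwards exceeds its earlier worst severity, or becomes serious, a new record is entered and dated from the worsening. The first record keeps the worst severity reached before that dose. Apply this to all patients who enter the OLE, whatever their blinded treatment, because section 8.1.2 keeps the transition blinded and sites cannot tell who was on placebo.
3. In 13.6.4.2, state that the new record counts as treatment emergent in the OLE.

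The same wording would settle the sustained step up on which the text is now silent. The cost is a few sentences in the protocol and the CRF completion guideline, and a few extra AE records. No visit, patient or treatment rule changes.
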